5.4 Handling of Missing Data

No data imputation will be performed for missing data.

6 Primary and Secondary Outcome Variables

6.1 Primary Outcome Variables

Time-matched difference between the OPC-61815 and placebo data in change from baseline for QTcF in 12-lead Holter ECG

6.2 Secondary Outcome Variables

12-lead Holter ECG parameters (heart rate, RR interval, PR interval, QRS interval, QT interval, and QTcF interval) and ECG waveform patterns

6.3 Pharmacokinetic Outcome Variables

Plasma concentrations and pharmacokinetic parameters of OPC-61815 free form and tolvaptan

6.4 Safety Outcome Variables

Adverse event reporting, clinical laboratory assessments, physical examination, vital signs (blood pressure, pulse rate, and body temperature), body weight, and 12-lead ECG

7 Disposition and Demographic Analysis

7.1 Subject Disposition

For subjects from whom informed consent was obtained (screened subjects), the number of subjects whom informed consent was obtained, the numbers and percentages of randomized subjects, subjects administered IMP, completed subjects after IMP administration, and discontinued subjects after IMP administration (the denominator indicates the number of randomized subjects) will be summarized as a whole and per sequence. For discontinued subjects after IMP administration, the number and percentage of subjects by reason for discontinuation will be summarized.

For randomized subjects, the number and percentage of subjects included in each statistical analysis set and central tendency analysis (11.1.1 Primary Endpoints Analysis) will be summarized as a whole and per sequence.

7.2 Demographic and Baseline Characteristics

For the pharmacodynamic analysis set and the safety analysis set, descriptive statistics (number of subjects, mean, standard deviation, minimum, median, and maximum) for age, height (cm), body weight (kg) at screening, and BMI (kg/m^2) will be calculated as a whole and per sequence.

7.3 Medical History

For the pharmacodynamic analysis set and the safety analysis set, frequency distribution (number of subjects, %) of the presence or absence of medical history and complications will be calculated as a whole and per sequence.

7.4 Treatment Compliance

For the pharmacodynamic analysis set and the safety analysis set, frequency distribution of subjects who satisfy all the following conditions for each treatment (OPC-61815 16 mg, OPC-61815 32 mg, placebo, or moxifloxacin) will be calculated by treatment as a whole and per sequence.

- Injection (OPC-61815 16 or 32 mg, or placebo)
 - Single intravenous administration over a period of 1 hour (allowable time range: 59 to 65 minutes) once daily in a fasting state.
 - Administration of full dose of IMP completed within allowable time range.
 - No interruption of administration from 30 minutes after the start.
- Tablet (moxifloxacin)
 - Administration of full dose of IMP completed.

7.5 Prior and Concomitant Medication

Prior and concomitant medications will not be tabulated in this trial.

7.6 Protocol Deviations

Protocol deviations will not be tabulated in this trial.

8 Efficacy Analyses

Not applicable.

9 Safety Analyses

The following analyses will be performed per treatment in the safety analysis set. The baseline will be the value before the start of IMP administration on Day 1 in each treatment period.

9.1 Extent of Exposure

The percentage of administered subjects to randomized subjects will be calculated.

9.2 Adverse Events

All adverse events (AEs) will be coded by system organ class (SOC) and preferred term (PT) (Medical Dictionary for Regulatory Activities [MedDRA]). The incidence of the following events will be summarized by all events, by SOC, and by PT:

- Treatment-emergent AEs (TEAEs)
- TEAEs by severity
- TEAEs with an outcome of death
- Serious TEAEs
- TEAEs leading to discontinuations of the IMP (calculated only when treatment is injection)

When the same AE occurs more than once during one treatment period in the same subject, the most severe event is included in incidence calculation. The incidence of TEAEs potentially causally related to IMP will also be summarized.

In Periods 1, 2, and 3, TEAEs are the events occurring after the start of IMP administration in each period until the start of IMP administration in the subsequent period. In Period 4, AEs that occur after the start of IMP are recorded as TEAEs.

9.3 Clinical Laboratory Data

For clinical laboratory data other than qualitative urine tests, descriptive statistics will be calculated for measurements and changes from baseline at each postdose time point. For qualitative urine test data, a shift table comparing test results at each postdose time point to baseline will be created. Each clinical laboratory test result other than qualitative urine tests will be categorized into “within normal,” “below the lower limit of normal,” and “above the upper limit of normal” using the trial site’s reference range to create a shift table of test results at each postdose time point compared to baseline.

9.4 Vital Sign Data and Body Weight

For each item (blood pressure, pulse rate, body temperature, and body weight), descriptive statistics will be calculated for measurements and changes from baseline at each postdose time point.

9.5 Physical Examination Data

Physical findings will not be tabulated in this trial.

9.6 Electrocardiogram Data

For each parameter (heart rate, RR interval, PR interval, QRS interval, QT interval and QTcF interval) of 12-lead electrocardiogram (ECG), descriptive statistics will be calculated for measurements and changes from baseline at each postdose time point. On normal/abnormal assessment, a shift table comparing data at each postdose time point to baseline will be created.

10 Pharmacokinetic Analyses

1) Endpoints

- a) Plasma OPC-61815 free form and tolvaptan (OPC-41061) concentrations
- b) PK parameters of plasma OPC-61815 free form and tolvaptan (OPC-41061)
 C_{max} , AUC_{24h} , AUC_t , AUC_{∞} , t_{max} , λ_z , $AUC_{\%Extrap}$, t_{last} , $t_{1/2,z}$, CL^a ,
 CL/BW^a , V_z^a , V_z/BW^a

^aCalculated for OPC-61815 only

2) Handling of Data

- a) Nonacceptance of data will be determined in accordance with the following conditions in this trial.
 - For each analyte, if blood sampling is conducted outside the time window for the analyses (see [Table 10-1](#) and [Table 10-2](#)), the data will be excluded from the calculation of descriptive statistics for plasma concentrations at that time point. However, it will be used for the

calculation of pharmacokinetic parameters, and if the calculation of pharmacokinetic parameters is determined to be unsuitable, the parameter will not be adopted.

Table 10-1 Acceptable Window for Analysis of OPC-61815 (Same in each period)		
	Time Point	Acceptable Window
Day 1	Predose	Within 3 hours before IMP administration
	1 hour	Within 2 minutes after end of administration
	1.5 hours	Specified time point + 2 minutes
	2 hours	Specified time point + 3 minutes
	3 hours	Specified time point + 5 minutes
	4 hours	Specified time point + 10 minutes
	6 and 12 hours	Specified time point + 15 minutes
Day 2	24 hours	Specified time point + 30 minutes

Table 10-2 Acceptable Window for Analysis of OPC-41061 (Same in each period)		
	Time Point	Acceptable Window
Day 1	Predose	Within 3 hours before IMP administration
	1 hour	Within 2 minutes after end of administration
	1.5 hours	Specified time point + 10 minutes
	2 hours	Specified time point + 10 minutes
	3 hours	Specified time point + 10 minutes
	4 hours	Specified time point + 10 minutes
	6 and 12 hours	Specified time point + 15 minutes
Day 2	24 hours	Specified time point + 30 minutes

- None of the plasma concentrations after use of drugs or food (see [Appendix 4](#)) which may inhibit or induce CYP3A4 activity will be used for calculating descriptive statistics at that time. Of the parameters calculated with data including plasma concentrations excluded from descriptive statistics, the parameters determined to be unsuitable for the calculations will not be adopted.
- For OPC-61815 injection 16 mg and 32 mg groups, in the case that IMP administration was not performed by the following administration method or in the event of missing a dose, the plasma concentrations on the period (treatment) will not be used for the calculation of descriptive statistics. The parameters calculated with data including plasma concentrations excluded from descriptive statistics will not be adopted.
 - Single intravenous administration over a period of 1 hour (allowable time range: 59 to 65 minutes) once daily in a fasting state
 - Administration of full dose of IMP completed within allowable time range.
 - No interruption of administration from 30 minutes after the start.

書式変更

- b) Plasma concentrations below lower limit of quantitation that occur prior to and after the first measurable concentration will be imputed to 0 (ng/mL) and as missing, respectively. Lower limit of quantitation of each analyte is listed in [Appendix 5](#).
- c) Concentrations reported as Not Analyzed (NA) or Not Determined (ND) are regarded as missing values.
- d) Unused concentrations and the unadopted parameters should be outputted in the list.
- e) Missing or unused concentrations and parameter values that cannot be calculated or adopted will not be used for tabulation.

3) Statistical analysis method

Descriptive statistics will be calculated in the following manner:

- a) Plasma drug concentration
 - At each blood collection time point, descriptive statistics will be calculated by analyte and treatment.
 - Descriptive statistics to be calculated for plasma drug concentration will be number of analyzed subjects, number of subjects included in the tabulation, arithmetic mean, standard deviation, coefficient of variation, minimum, median, and maximum. However, descriptive statistics will be calculated only at the time point when the number of subjects included in the tabulation exceeds half of the number of analyzed subjects.
- b) Plasma pharmacokinetic parameters excluding λ_z , $\lambda_z(\text{lower})$, $\lambda_z(\text{upper})$, $\lambda_z(\text{point})$, and $\lambda_z(\text{Rsqr})$
 - Descriptive statistics will be calculated for each parameter by analyte and treatment.
 - Descriptive statistics to be calculated for plasma drug concentration will be number of analyzed subjects, number of subjects included in the tabulation, arithmetic mean, standard deviation, coefficient of variation, geometric mean, minimum, median, and maximum. However, descriptive statistics will be calculated only when the number of subjects included in the tabulation exceeds half of the number of analyzed subjects.

10.1 Statistical Analyses of Primary Pharmacokinetic Endpoints

Not applicable.

10.2 Statistical Analyses of Secondary Pharmacokinetic Endpoints

Not applicable.

10.3 Technical Details of Pharmacokinetic Statistical Analyses

Not applicable.

10.4 Pharmacokinetic and Pharmacodynamic Analyses

For subjects who have QT data and plasma OPC-61815 concentration data after administration of OPC-61815 (adopted concentration at 10 Pharmacokinetic Analyses 2) Handling of Data), as well as QT data after placebo administration at the matching time points, differences between OPC-61815 and placebo in change in QTcF interval from baseline at the matching time points are analyzed. A linear mixed-effects model is used, taking plasma OPC-61815 concentration as a fixed effect and subject as a random effect (slope and intercept), to estimate the intercept and the coefficient of plasma OPC-61815 concentration. A scatter plot of plasma OPC-61815 concentrations (horizontal axis) and the time-matched differences (vertical axis) between the OPC-61815 and placebo data in change from baseline for QTcF will be created and a regression line will be plotted.

SAS code is shown below.

```
proc mixed method=reml;
  class subject;
  model corrected_QTcF = conc / s alpha=0.05;
  random int conc / subject=subject type=vc;
run;
```

11 Pharmacodynamic Analyses

12-lead Holter ECG data will be used. For each parameter, the mean (rounded integer value in each unit [beats/min, msec]) of measurements from 3 predose time points (1 hour, 30 minutes, and 15 minutes before IMP administration) in each period will be used as the baseline value. If missing is occurred at any of 3 predose time points in each period, a mean value will be calculated using the points at which the values were obtained and will be used as the baseline value. Changes from baseline in corresponding period will be calculated at each postdose time point.

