6.2 Pharmacodynamic Methods

12-lead Holter ECG parameters will be analyzed at a central ECG laboratory. The central laboratory will obtain 3 snapshots for each scheduled ECG from the 12-lead Holter ECG data sent from the trial site, determine the ECG parameters (heart rate, RR interval, PR interval, QRS interval, QT interval, and QTcF interval), and assess waveform patterns. Time windows for data capture are presented in Table 6.2-1. Each data capture will be obtained at an interval of at least 1 minute. The mean from 3 captures will be recorded as the value for each ECG measurement.

Schedule for 12-lead Holter ECG Data Capture^a		Time Window
Day 1	1 hour before IMP administration	Within –5 minutes
	30 minutes before IMP administration	
	15 minutes before IMP administration	
	1 hour after start of IMP administration	Within 5 minutes before end of IMP administration ^b
	1.5 hours after start of IMP administration	Within –5 minutes
	2 hours after start of IMP administration	
	3 hours after start of IMP administration	
	4 hours after start of IMP administration	
	6 hours after start of IMP administration	
12 hours after start of IMP administration		
Day 2	24 hours after start of Day 1 IMP administration	

^a: For moxifloxacin, “IMP administration” instead of “start of IMP administration” in the above table

^b: “Within –5 minutes” for moxifloxacin

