6.3 Pharmacokinetic/Pharmacodynamic Methods

For subjects who have QT data and plasma OPC-61815 concentration data after administration of OPC-61815, as well as QT data after placebo administration at the matching time points, differences between OPC-61815 and placebo in change in QTcF interval from baseline at the matching time points are analyzed. A linear mixed-effects model is used, taking plasma OPC-61815 concentration as a fixed effect and subject as a random effect, to investigate the relationships between plasma OPC-61815 concentration and pharmacodynamic parameters.

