11.1 Primary and Secondary Endpoint Analyses

11.1.1 Primary Endpoint Analyses

The primary endpoint is the time-matched difference between the OPC-61815 and placebo data in change from baseline for QTcF in 12-lead Holter ECG. Central tendency analysis for OPC-61815 will be performed for subjects in the pharmacodynamic analysis set who appropriately completed all IMP treatments (OPC-61815 16 mg, OPC-61815 32 mg, placebo, and moxifloxacin) (ie, in whom the administration of the injections was completed within the time windows presented in Protocol 3.2 Trial Treatments [the duration of intravenous administration of OPC-61815 16 mg or 32 mg or placebo: 59 to

65 minutes] without interruption of administration from 30 minutes after the start, as well as the condition described in 7.4 Treatment Compliance) and for whom predose and postdose QT data are available for all 4 treatment periods.

For each OPC-61815 dose (16 mg and 32 mg), the upper limit of the CI for the time-matched difference in the least squares mean for the change in QTcF from baseline compared to the placebo data will be evaluated to determine if it is lower than 10 msec at all postdose time points using the hypothesis presented below. Because the alternative hypothesis is an intersection hypothesis, the 2-sided 90% CI (1-sided 95%) will be calculated without type 1 error adjustment.

$$H_0: \bigcup \{\mu_{A(i)} - \mu_{P(i)} \geq 10\}, i = 1, 2, \dots, 8$$

$$H_1: \bigcap \{\mu_{A(i)} - \mu_{P(i)} < 10\}, i = 1, 2, \dots, 8$$

$\mu_{A(i)}$: Mean change from baseline in QTcF interval at time i after OPC-61815 administration

$\mu_{P(i)}$: Mean change from baseline in QTcF interval at time i after placebo administration
 $i = 1, 2, \dots, 8$ respectively correspond to 1, 1.5, 2, 3, 4, 6, 12, and 24 hours after start of IMP administration

Using a linear mixed effect model with baseline QTcF in each treatment period as a covariate, treatment, sequence, treatment period, time point, and interaction between treatment and time point as fixed effects, and subject as a random effect, point estimates and CIs for the time-matched difference in the least squares mean for the change in QTcF from baseline compared to the placebo data will be calculated.

SAS code is shown below. The data set will include all 4 treatments data.

```
proc mixed method=reml;  
  class treatment subject time arm period;  
  model change = arm period treatment time treatment*time baseline/ s ddfm=satterth;  

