  random subject(arm);  
  lsmeans treatment*time/diff pdiff cl alpha=0.1;  
run;
```

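### Does the concentration–QTcF model in SAP 10.4 need a predicted effect at each dose's Cmax with a 90% confidence interval?

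*SAP*

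**What the plan says.** Protocol 6.3 gives the aim of the model: "to investigate the relationships between plasma OPC-61815 concentration and pharmacodynamic parameters". SAP 10.4 carries this out with a mixed model of the time-matched, placebo-corrected QTcF change on OPC-61815 concentration, with intercept and slope random by subject. The stated purpose is "to estimate the intercept and the coefficient of plasma OPC-61815 concentration", followed by a scatter plot and regression line. The model line of the code is "model corrected_QTcF = conc / s alpha=0.05". No statement in that code asks for a prediction at a named concentration or for the covariance of the two coefficients.

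The primary analysis in SAP 11.1.1 is specified differently. Its text says that "the 2-sided 90% CI (1-sided 95%) will be calculated without type 1 error adjustment", and its code contains "lsmeans treatment*time/diff pdiff cl alpha=0.1". The criterion is an upper limit below 10 msec at all eight postdose times, for each dose separately. Table 6.2-1 of the protocol (section 6.2) places the 1-hour ECG capture for the infusions "Within 5 minutes before end of IMP administration".

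**The concern.** An exposure–response model in a QT study is most easily read as a predicted effect in msec at a relevant concentration, with an interval on the same 90% basis as the main criterion. SAP 10.4 stops at the coefficients. Its only stated level is 0.05, which can concern at most limits for the individual coefficients, not a prediction.

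A reader can form the point prediction by hand from the intercept, the slope and the geometric mean Cmax, which SAP 10 plans to report. The interval is another matter. Intercept and slope are negatively correlated, so combining their standard errors as if they were independent gives too wide an interval. Protocol 2.2.2 argues for 16 and 32 mg in terms of exposure in heart-failure patients, so the one analysis that links QTcF to exposure seems to end before its useful result. If the trial's QT conclusion depended on this model, that would be a real weakness.

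**Working it through.** **What the plan needs from the model.** Set side by side, the passages assign different tasks:

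- Protocol 6.3: investigate the relationship. SAP 10.4: intercept, slope, plot, line. The second delivers the first.
- SAP 11.1.1: decide whether the effect stays below 10 msec, for each dose at each time, with 90% intervals. This is where the decision is made.
- Protocol 3.7.6.1.1 puts the expected tmax of OPC-61815 free form at 1 hour after the start. The 1-hour ECG is captured at the end of infusion (Table 6.2-1). The 1-hour primary contrast is therefore already a test near Cmax, for both doses.

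**Inputs.** Within-subject SD 7.86, assumed OPC-61815 effect 3.0 msec, 45 evaluable subjects and 5% discontinuation (SAP 4). Free-form half-life 0.63 to 1.7 h (Protocol 1.2.1). The documents give no concentrations for this 1-hour regimen and no correlation between time points. Assumed: mono-exponential decline after 1 hour with half-life 0.63, 1.0, 1.3 or 1.7 h, within-period correlation 0, 0.3, 0.5 or 0.7, and data to 4, 6 or 24 h (4 × 4 × 3 = 48 scenarios).

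**The plan's own figure.** With SE = 7.86 × √(2/n), a paired t test on n − 1 df, a distance of 10 − 3 = 7 msec, 1-sided 0.05 and 16 independent comparisons (8 times × 2 doses), the joint probability is 0.896 at n = 44 and 0.909 at n = 45. So 45 is reproduced, and 45/0.95 = 47.4 gives 48. The concentration model plays no part in it.

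**Precision of the primary 1-hour contrast.** SE = 7.86 × √(2/45) = 1.657 msec. The 90% half-width is 1.645 × 1.657 = 2.73 msec. At a true effect of 3.0 the expected upper limit is 3.0 + 2.73 = 5.73 msec.

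**Precision of a model prediction at the 32 mg Cmax.** For intercept a and slope b,

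Var(a + b·Cmax) = Var(a) + Cmax²·Var(b) + 2·Cmax·Cov(a, b).

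The covariance of the coefficients is B V Bᵀ/45, with B = (XᵀX)⁻¹Xᵀ, where X holds the intercept and the concentrations at both doses. V is 7.86² times the block matrix [[2R, R], [R, 2R]], since both doses share the placebo values, and R is the correlation matrix over time points.

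| Quantity (48 scenarios) | SE, msec | 1.645 × SE | Upper limit at effect 3.0 |
|---|---|---|---|
| Primary contrast, one time point | 1.657 | 2.73 | 5.73 |
| Model prediction, covariance used | 1.194–1.638 | 1.96–2.69 | 4.96–5.69 |
| Model prediction, covariance ignored | 1.678–2.592 | 2.76–4.26 | 5.76–7.26 |

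The gain over the primary contrast is 1 − 1.638/1.657 = 1% to 1 − 1.194/1.657 = 28%. The 28% needs the 12- and 24-hour values. Protocol 1.2.1 reports the free form below quantitation by 8 hours in every dose group, and SAP 10 sets such later values to missing. With data to 4 or 6 h only, the smallest SE is 1.241 and the gain at most 25%. When the planned mixed model was fitted to simulated data (half-life 1.7 h, correlation 0.7, data to 6 h, 25% between-subject spread in exposure), the model SE averaged 1.676, slightly worse than the single contrast.

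**Cost of a wrong hand calculation.** Ignoring the covariance inflates the SE by a factor of 1.10 to 1.91. The error is on the cautious side. At the assumed effect, even the widest rebuilt upper limit is 7.26 msec, below 10.

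**The case for a change.** The strongest case for the concern is that its technical core is right. The code gives no interval at any exposure, and none can be recovered from the printed coefficients. The addition would cost two lines, and naming the concentration and the level in advance would prevent a later data-driven choice. All of that stands. The misreading could also show in some results: in the widest scenario, a point estimate between 10 − 4.26 = 5.74 and 10 − 2.73 = 7.27 msec would pass the primary contrast while a wrongly rebuilt interval crossed 10. But no rule in either document refers to such an interval, and the sponsor can obtain the correct one by refitting the same data.

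The appeal to exposure is weaker than it looks. The target exposures in Protocol 2.2.2 are those that 16 and 32 mg were chosen to produce, and both doses are tested directly. What the primary contrasts cannot give is an interval at some other concentration, between or below the two peaks. Predictions at the two Cmax values would not give that either.

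One argument against the extra interval should not be used. The model ignores that both doses share placebo values, so one might expect its interval to be too narrow. Small simulations pointed that way, but a larger one did not confirm it. With 700 simulated trials for each of four half-life/correlation pairs (1.0/0, 1.3/0.3, 1.3/0.5 and 1.7/0.7; data to 6 h; 25% exposure spread), the nominal 90% interval covered the true value in 90 to 91% of trials. The interval would be usable. It is simply not needed for what this plan sets out to decide.

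**Conclusion.** The concern does not hold as a fault in the plan. SAP 10.4 delivers what Protocol 6.3 asks for, no passage is contradicted, and no decision depends on the model. The effect near Cmax is already estimated for each dose with a 90% interval against 10 msec, at a half-width of about 2.7 msec if the SD of 7.86 and 45 evaluable subjects hold. A model prediction at the 32 mg Cmax would be about as precise, or up to about a quarter better where late samples are below quantitation, and would leave the primary conclusion and the 48 subjects unchanged. These precision figures rest on assumed concentrations and correlations; the reading of the text does not. The list of summary tables (SAP Appendix 2) is not in the supplied text, so it cannot be excluded that such a table is planned there. Adding the prediction is a matter of preference.
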